7.7.6 Echocardiograms/Multigated Acquisition Scans

Echocardiogram or multi-gated acquisition results will be presented in a data listing. In addition to descriptive statistics of observed data, the number and percent of subject with LVEF values below 50% will be presented.

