¹⁴ ECHO is the preferred methodology to measure LVEF. MUGA may be used if ECHO is not available or not technically feasible. However, the same methodology should be used throughout the study. Assessments should be performed during screening, on C2D1 (+7 days), EOT, and if clinically indicated at any point. If a subject does not complete 2 cycles of study treatment, the EOT assessment of LVEF is not required unless clinical signs or symptoms warrant an examination. All subjects who require dose reduction of study treatment due to decrease in LVEF should have ECHO at the end of each cycle for 2 more cycles and then if clinically indicated to ensure that subject is not experiencing a decrease in LVEF even with a reduced dose.

¹⁵ ECOG PS to be assessed at screening, C1D1, C1D15, and D1 of each subsequent cycle beginning at C2, and at EOT. During the Extended-Use phase, ECOG PS will be assessed according to local standards of care.

¹⁶ Ophthalmic examination if clinically indicated, including full fundoscopic examination and optical coherence tomography should be performed by an ophthalmologist. Additional examinations should be performed as clinically indicated.

¹⁷ Monitor and record AEs and SAEs throughout the main study. Record all AEs, regardless of relationship to study treatment, that occur after initiation of first study treatment until EOT. All AEs and SAEs will be collected from the start of treatment until 30 days after the last dose, or upon initiation of alternative cancer treatment, whichever occurs first. After this period, investigators should report only SAEs that are thought to be related to RMC 4630 and/or sotorasib. After informed consent, but prior to initiation of study treatment, only SAEs caused by a protocol mandated intervention will be collected (eg, SAEs related to invasive procedures such as biopsies or medication washout). All SAEs that occur should be reported to the Sponsor or designee within 24 hours of investigator awareness. All AEs (regardless of relationship to study treatment) and SAEs determined not to be study- treatment related (ie, not related and unlikely related)

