5.2. Exclusion Criteria

If a subject meets **ANY** of the following criteria, he or she will be excluded from study participation:

1. Subject has primary central nervous system (CNS) tumor(s)
2. Subject has known or suspected leptomeningeal or brain metastases or spinal cord compression. However, subjects who were previously treated for these conditions who have had stable CNS disease (no evidence of clinical and radiographic disease progression and asymptomatic in the absence of corticosteroids or anti-convulsant

therapy) are eligible to participate in the study, as long as SD is documented by a brain magnetic resonance imaging (MRI) performed within 28 days of C1D1.

3. Subject who has any of the following cardiac abnormalities:
 - a. Medically uncontrolled hypertension (≥ 160 mmHg systolic blood pressure or ≥ 100 mm Hg diastolic blood pressure)
 - b. Congestive heart failure Class ≥ 2 , as defined by the New York Heart Association
 - c. Acute coronary syndrome (including unstable angina, coronary artery stenting, or angioplasty, bypass grafting within prior 6 months); myocardial infarction within 6 months of informed consent.
 - d. History or evidence of current, uncontrolled, clinically significant, unstable arrhythmias
 - i. Subject with medically controlled atrial fibrillation >1 month prior to Study Day 1 is eligible.
 - ii. Subject who has a pacemaker in place to control atrial arrhythmias is a candidate for the study.
 - e. History of congenital long QT syndrome or prolonged corrected QT interval (QTc) >470 msec for females and > 450 msec for males using Fridericia's formula (unless a pacemaker is in place) or uncorrectable abnormalities in serum electrolytes (ie, sodium, potassium, calcium, magnesium, phosphorus):
 - i. Subject may use average of triplicate readings for assessing QTc interval.
 - ii. Subject with an implantable defibrillator is not eligible to participate in the study.
 - f. Current cardiomyopathy or history within in the past 12 months prior to informed consent.
 - g. Baseline left ventricular ejection fraction (LVEF) below the institutional lower limit of normal (LLN) or $<50\%$, whichever is lower.
4. Any prior history of (or active) ILD or pneumonitis, or prior thoracic radiotherapy within 2 months of enrollment.

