8.2.5. Echocardiograms/Multigated Acquisition Scans

All subjects must have their LVEF assessed by two-dimensional ECHO scan or MUGA scan as part of the screening procedure and as outlined in the SoA ([Table 1](#)). If a subject does not complete 2 cycles of study treatment, the EOT assessment for LVEF is not required, unless clinical signs or symptoms warrant additional imaging.

ECHO is the preferred method since it can detect wall motion abnormalities. However, in situations where an ECHO machine is not readily available or is technically limited, a MUGA scan may be obtained to evaluate LVEF. The same methodology should be used throughout the study and, to the greatest extent possible, at the same institution/facility.

The LVEF is to be calculated based on institutional guidelines and must be within institutional normal limits or 50%, whichever is lower, before a subject can enroll into the study. The LLN for the LVEF at the institution/facility should be recorded on the respective eCRF along with the LVEF result.

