7.7.5 Electrocardiograms (ECG) and QTcF Interval

Baseline is defined as the last non-missing measurement on or prior to the first dose of study drug.

The QTcF and ECG overall interpretation (normal, abnormal not clinically significant [NCS], abnormal clinically significant [CS]) will also be summarized for baseline and change from baseline to EOT [expressed as Improvement, No Change, and Deterioration] by dose level, where:

- Improvement = Abnormal CS to Abnormal NCS/Normal or Abnormal NCS to Normal;
- Deterioration = Normal to Abnormal NCS/CS, Normal/Abnormal NCS to Abnormal CS
- No change = Normal to Normal, Abnormal NCS to Abnormal NCS, Abnormal CS to Abnormal CS.

In addition, the QTcF values for baseline, actual values and changes from baseline at each post baseline visit will be summarized by dose level using descriptive statistics.

The frequency and percentage of the maximum post-baseline QTcF values classified in accordance with the ICH E14 boundaries will be presented:

Table 1: QTcF / QTcB Interval ICH E14 Boundaries

QTcF / QTcB Interval	Criteria (msec)
Maximum Observed QTcF / QTcB interval	≤ 450 msec > 450 msec > 480 msec > 500 msec
Maximum Change from baseline in QTcF / QTcB interval	≤ 30 msec > 30 to ≤ 60 msec > 60 msec

A listing of all ECG data including individual and calculated mean of triplicate measurements, derived change from baseline will be provided using the treated population, along with demographic information of age and sex. Any value outside the clinical reference range will be flagged.

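### SAP 7.7.6 summarises LVEF as observed values and an absolute count below 50%, with no change from baseline, so a large fall that stays at or above 50% is not counted.

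*SAP*

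**What the plan says.** **SAP 7.7.6** contains the whole LVEF analysis. It states that "Echocardiogram or multi-gated acquisition results will be presented in a data listing". It then adds summary statistics of the observed data and says that "the number and percent of subject with LVEF values below 50% will be presented". It does not say that the count is post-baseline, does not relate it to the subject's starting value, and plans no change from baseline. SAP 7.1 defines a baseline for general use, but 7.7.6 does not call on it.

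**Protocol entry rule.** Exclusion criterion 3g (Section 5.2) and Section 8.2.5 set the same limit. In 8.2.5, LVEF "must be within institutional normal limits or 50%, whichever is lower, before a subject can enroll into the study".

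**Protocol data collection.** Table 1, footnote 14, gives the schedule: "Assessments should be performed during screening, on C2D1 (+7 days), EOT, and if clinically indicated at any point". Section 8.2.5 adds: "The LLN for the LVEF at the institution/facility should be recorded on the respective eCRF along with the LVEF result". The baseline value and the local reference limit are therefore both collected.

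**Protocol concern.** The same footnote foresees dose reduction because LVEF has decreased, with further echocardiograms afterwards. Section 2.2.2.1 lists left ventricular dysfunction among toxicities reported with more than one RAS-pathway inhibitor.

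**The concern.** The protocol watches for a decrease, but the SAP tabulates a level. A count of values below a fixed cut-off answers a different question from how many subjects lost ventricular function on treatment. It can be zero when several subjects have fallen substantially within the range above 50%. If subjects may enter below 50%, it can also be above zero when nobody has changed.

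The neighbouring SAP sections avoid this. Section 7.7.1 tabulates laboratory shifts from baseline to the worst post-baseline grade. Section 7.7.4 summarises selected vital signs as actual values and as change from baseline. Section 7.7.5 gives QTcF change by visit and in categories. LVEF is the exception, and no reason is given. At stake is whether the report can describe a cardiac safety measurement in a single-arm study, where the subject's own baseline is the only within-study reference.

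**Working it through.** The plan states no figure to reproduce here. The check applies the documents' rules to example subjects. The LVEF and LLN values below are assumptions chosen for illustration; the rules are not.

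**Rules**
- Admitted if baseline LVEF ≥ min(institutional LLN, 50%) (Protocol 5.2, criterion 3g, and 8.2.5).
- On-treatment value counted if LVEF < 50% (SAP 7.7.6).
- Change = post-baseline value − baseline value (not planned in SAP 7.7.6).

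| Baseline | Post-baseline | LLN | Admitted? | Post-baseline value counted? | Change (points) |
|---|---|---|---|---|---|
| 70% | 51% | 50% | yes | no | −19 |
| 70% | 52% | 50% | yes | no | −18 |
| 65% | 50% | 50% | yes | no | −15 |
| 52% | 49% | 50% | yes | yes | −3 |
| 48% | 48% | 45% | yes | yes | 0 |
| 48% | 50% | 45% | yes | no | +2 |
| 48% | 48% | 50% or 55% | no | – | – |

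**Missed falls.** The first three rows fall by 15 to 19 points and are not counted; the fourth falls by 3 and is. This needs no assumption about an LLN below 50%. If the LLN were 55%, the subject falling from 70% to 51% would also have moved from above to below the local normal limit and would still not be counted.

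**Entry below 50%.** The fifth row is counted with no change. In the sixth row the on-treatment value is not below 50%, but because the count is not limited to post-baseline values, the screening value of 48% could still bring the subject in. Both cases require min(LLN, 50%) < 50%, that is, LLN < 50%. The last row shows that with an LLN of 50% or more nobody below 50% can enter, so there is no overlap.

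**Size.** SAP 2.3 anticipates 20 to 40 subjects at the final expansion dose. One subject is 1/20 = 5% or 1/40 = 2.5% of such a group. How many subjects are affected cannot be derived, because the documents give neither LLN values nor an LVEF distribution.

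**Whether the other summaries fill the gap.** The scheduled LVEF times are screening, C2D1 and EOT. Footnote 14 does not require the EOT scan for subjects who do not complete 2 cycles. Statistics by visit would therefore rest on different sets of subjects, and the difference between visit means is not a mean of paired changes.

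**The case against.** The strongest reply has four parts.

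1. **Analysis by visit.** SAP 6.1 analyses data by nominal scheduled visit, and table layouts sit in separate shells that are not available here. The 50% count may well be shown by visit, with screening apart from on-treatment values. That is a fair reading and would ease the problem of subjects who entered below 50%. It would still give no paired change and no count of newly abnormal subjects.

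2. **Other routes into the report.** All results are listed. Protocol Appendix 3 makes a clinically significant worsening on a safety assessment an adverse event, and SAP 7.7.3 tabulates adverse events, including those leading to dose reduction. This stands. A reader might infer that LVEF falls would go unseen; the documents do not support that. It is the summary count that misses them.

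3. **Unknown LLN.** A reader might infer that the entry criteria do admit subjects below 50% and so inflate the count. The documents show only that this is possible where the LLN is below 50%. No site is shown to have such a limit.

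4. **Modest importance.** LVEF is not named among the secondary endpoints and no hypothesis is tested. This stands, and it limits the weight of the point.

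It is also tempting to extend the criticism to QTcF, since women may enter at up to 470 msec and the threshold table starts at 450 msec. The documents do not support that. SAP 7.7.5 says: "The frequency and percentage of the maximum post-baseline QTcF values classified in accordance with the ICH E14 boundaries will be presented". The same table classifies maximum change from baseline (≤30, >30 to ≤60, >60 msec), and change is summarised at each visit. A woman going from 465 to 463 msec appears above 450 but also in the ≤30 change row. A man going from 385 to 448 msec (+63) is caught in the >60 row. The >480 and >500 rows lie above the entry limits except for subjects with a pacemaker.

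**Conclusion.** The point holds for LVEF and only for LVEF. As written, SAP 7.7.6 gives no change from baseline and no post-baseline restriction on its only threshold count. That the count misses large falls ending at or above 50% follows directly from the rule. That it may include subjects who entered below 50% is conditional on a site LLN under 50%, and the number is unknown. The 2.5 to 5 percentage points is the weight of one subject in a group of 40 or 20, not an estimate of bias.

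The point is minor. It does not touch the primary endpoint, and the listing and adverse event tables remain as a backstop. It is worth correcting because a better summary can be made from data already collected. The conclusion rests on the SAP text; table shells or programming specifications not seen here could already contain part of the remedy.

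**What to change.** In SAP 7.7.6:

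- Limit the below-50% count to post-baseline values and show it by baseline status (at or above 50%, below 50%).
- Add change from baseline to the lowest post-baseline LVEF, summarised descriptively. If a category for the size of the fall is wanted, the sponsor should choose the cut in advance; the documents do not supply one.
- Count subjects with a post-baseline LVEF below the institutional LLN recorded on the eCRF who were at or above it at baseline.
- State the denominator (subjects with a baseline and at least one post-baseline value), and state that unscheduled scans count towards the lowest value. SAP 6.1 currently makes that exception only for laboratory shifts.

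The cost is a few lines of SAP text and one revised table. Baseline LVEF, on-treatment LVEF and the LLN are already collected. No change to QTcF is needed; a cross-tabulation of the >450 msec row by baseline would be an optional matter of presentation.

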7.7.7 Eastern Clinical Oncology Group Performance Status (ECOG PS)

Data listing of ECOG PS results will be provided.

7.7.8 Physical Examinations

Data listing of physical examinations data will be provided.

7.8 Pharmacokinetics Analyses

Concentrations of RMC-4630 and sotorasib will be summarized descriptively by timepoint as part of the main CSR. Concentrations of RMC-4630 may be used for population PK analysis and presented in a separate report. PK of RMC-4630 may be used for integrated E-R analysis and reported separately.

7.9 Exploratory Analyses

Biomarker exploratory analyses may be described in a separate analysis plan and may be summarized in a report separate from the clinical study report.

8. Interim Analyses

No formal interim analysis will be conducted. However, as this is an open-label study, several analyses may be conducted at specific points during the study as well as at the end of the study.

9. Deviations from Statistical Analysis Plan

Any deviations from this statistical plan will be described and justified in the final clinical study report.

10. Significant Changes from the Protocol-specified Analyses

There have been no other changes in analyses from those defined in the protocol.

11. References

- 3 ICH. Statistical Principles for Clinical Trials, Guideline E9, 1998. Available at https://www.ich.org/fileadmin/Public_Web_Site/ICH_Products/Guidelines/Efficacy/E9/Step4/E9_Guideline.pdf
- 4 CPMP. Points to Consider on Missing Data. EMEA: London, 2001. Available at https://www.ema.europa.eu/en/documents/scientific-guideline/points-consider-missing-data_en.pdf
- 5 Guidance for Industry Clinical Trial Endpoints for the Approval of Cancer Drugs and Biologics, May 2007.
- 6 Guidance for Industry ICH. *E14 Clinical Evaluation of QT/QTc Interval Prolongation and Proarrhythmic Potential for Non-Antiarrhythmic Drugs*. 12 May 2005.
- 7 SAS Institute Inc., Cary, NC, USA.

12. Appendices

Appendix A1. Source Documents

The SAP was written based on the following documentation:

Document	Date	Version
Protocol	21 March 2022	V3.0
Protocol	21 November 2022	V4.0
eCRF	20 January 2023	V6

Appendix A2. Document History

Status and Version	Date of Change	Summary/Reason for Changes
Final Version 1.0	18 April 2023	NA; the first version, based on Protocol V4.0

Appendix B. Safety Laboratory Tests: Identifying Worst Values

Laboratory Test	Direction of Interest for Worst Case Values
HEMATOLOGY	
RBC Count	Low
Hemoglobin	Low
Hematocrit	Low
Platelet Count	Low
MCV	Low
MCH	Low
WBC Count	Low and High
Neutrophils	Low and High
Lymphocytes	Low and High
Monocytes	High
Eosinophils	High
Basophils	High
CHEMISTRY	
Sodium	Low and High
Potassium	Low and High
Chloride	Low
Bicarbonate	Low
BUN (Blood Urea Nitrogen)	Low and High
Creatinine	High
Glucose (non-fasting)	Low and High
Total Protein	Low
Albumin	Low
Phosphate	Low
Calcium	Low and High
Magnesium	Low
Uric Acid	High
Direct Bilirubin	High
LIVER SAFETY TESTS	
GGT	High
ALT (SGPT)	High
AST (SGOT)	High
Total Bilirubin	High
ALP	High
COAGULATION TESTS	
INR	High
PT	High
aPTT	High
PTT	High
